# 4.4.1.1.7 **Ongoing**

Ongoing is derived from the last daily intensity of the solicited period computed as described in Section 4.4.1.1.1 and the maximum intensity on the ongoing period. The Investigator's ongoing flag is not used because the measurement would determine the ongoing status of the reaction.

If the last daily intensity at D07 of the solicited period is at least Grade 1 and maximum intensity on the ongoing period is also at least Grade 1, then the reaction is considered ongoing. In any other cases the reaction will not be considered as ongoing.

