### 9.3.2.3.2 Reactogenicity (Solicited Reactions From Day 0 to Day 7 After Vaccination)

After vaccination of subjects, subject's parent(s)/legally acceptable representative(s) will be provided with a diary card, a digital thermometer, and a flexible ruler, and will be instructed how to use them. The following items will be recorded by the subjects in the diary card on the day of vaccination and for the next 7 days (ie, Day 0 through Day 7) until resolution:

- Daily temperature, with the route by which it was taken
- Daily measurement or intensity grade of all other solicited injection site and systemic reactions
- Action taken for each event (eg, medication)

The action(s) taken by the subject's parent(s)/legally acceptable representative(s) to treat and/or manage any **solicited reactions** will be classified in the CRB using the following list (all applicable items should be checked):

- None
- Medication
- Health care provider contact
- Hospitalized

The subject's parent(s)/legally acceptable representative(s) will be contacted by telephone 8 days (+ 2 days) after vaccination to remind them to record all safety information in the diary card.

If the timing of the TC should fall on a weekend or a holiday, the call should be made on the next business day. If contact is not made on the designated day, study staff will continue calling until contact is made. Every telephone attempt and its outcome will be documented in the source document.

Table 9.1 and Table 9.2 present, respectively, the injection site reactions and systemic reactions that are pre-listed in the diary cards and CRB, together with the intensity scales.

Table 9.1: Solicited injection site reactions: terminology, definitions, and intensity scales

CRB term (MedDRA lowest level term [LLT])	Injection site tenderness	Injection site erythema	Injection site swelling
Diary card term	Tenderness	Redness	Swelling
Definition	Pain when the injection site is touched or injected limb mobilized	Presence of a redness including the approximate point of needle entry	Swelling at or near the injection site  Swelling or edema is caused by a fluid infiltration in tissue or cavity and, depending on the space available for the fluid to disperse, swelling may be either soft (typically) or firm (less typical) to touch and thus can be best described by looking at the size of the swelling

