# 4.4 Derived Endpoints: Calculation Methods

# **4.4.1** Safety

#### 4.4.1.1 Solicited Reactions

# 4.4.1.1.1 Daily Intensity

All daily records for solicited reactions will be derived into daily intensity according to the following classification: None, Grade 1, Grade 2, Grade 3, or Missing.

For the derivation of daily intensities, the following sequential steps will be applied:

- 1) Solicited reactions (except Fever) with an Investigator presence recorded as "No" and with all daily records missing then all daily intensities will be derived as None.
- 2) For a temperature partially missing after decimal point, the data will be analyzed replacing "MD" (missing data) by zero. For example, a "39.MD" daily temperature will be considered as "39.0°C" at the time of analysis.
- 3) For non-measurable solicited reactions, daily intensities will correspond to daily records reported in the clinical database. For measurable solicited reactions the daily measurements reported in the clinical database will be converted based upon the intensity scales defined in the protocol; this assumes a reaction that is too large to measure (non measurable, "NM") is Grade 3.

Note: The maximum intensity on the ongoing period is derived from the record of the maximum intensity/measurement after the end of the solicited period following the rule described above.

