#### 4.4.1.1.6 Overall Number of Days of Occurrence

If a reaction is ongoing at the end of the solicited period, then the overall number of days of occurrence is derived from the daily intensities and the stop date of the reaction after the end of the solicited period. The overall number of days of occurrence is:

• (stop date – vaccination date) + (number of days of occurrence within the solicited period) – length of the solicited period + 1

If the stop date is missing or incomplete (contains MD), the overall number of days of occurrence will be considered as Missing.

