# **5.3.1.4** Intensity

For solicited reactions, missing intensities will be handled as described in Section 4.4.1.1.1. For unsolicited non-serious AEs, missing intensities will remain missing and will not be imputed.

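### A solicited reaction with a recorded stop date after D07 is classed as not ongoing when either the D07 grade or the post-D7 grade is missing, so the stop date is never used

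*SAP*

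**What the plan says.** SAP 4.4.1.1.1 derives each daily intensity as "None, Grade 1, Grade 2, Grade 3, or Missing", so Missing is a category distinct from None. The grade after D7 comes from a single record: "The maximum intensity on the ongoing period is derived from the record of the maximum intensity/measurement after the end of the solicited period".

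SAP 4.4.1.1.7 sets the test for ongoing status, with the same Grade 1 threshold for both records: "If the last daily intensity at D07 of the solicited period is at least Grade 1 and maximum intensity on the ongoing period is also" (the threshold is then repeated). It then closes the list: "In any other cases the reaction will not be considered as ongoing". The Investigator's own assessment is set aside on purpose: "The Investigator's ongoing flag is not used because the measurement would determine the ongoing status of the reaction".

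SAP 4.4.1.1.6 brings in the stop date, together with the daily grades, only after that test is passed: "If a reaction is ongoing at the end of the solicited period, then the overall number of days of occurrence is derived from the daily" (the sentence goes on to name both sources). If the stop date is missing or incomplete, the overall number of days is set to Missing.

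On missing grades, SAP 5.3.1.4 says only this: "For solicited reactions, missing intensities will be handled as described in Section 4.4.1.1.1". That section fills gaps in three situations: all daily records missing with Investigator presence recorded as No, a missing temperature decimal, and a reaction too large to measure. None of these covers a single blank D07 record or a blank post-D7 record. SAP 5.3.1 adds that nothing is replaced.

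Protocol 9.3.2.3.2 asks for recording "on the day of vaccination and for the next 7 days (ie, Day 0 through Day 7) until resolution", so information beyond D7 is meant to be collected.

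**The concern.** The rule reads the absence of a grade as evidence against an ongoing reaction. The reason given for ignoring the Investigator's flag is that the measurement decides the matter, but that reason fails when there is no measurement.

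The handling is also uneven. A missing stop date makes the overall duration Missing. A missing grade makes the reaction not ongoing, and a stop date that is present is then left out.

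What is at stake is the description of the longest solicited reactions: how many were still present after D7, and how long they lasted overall.

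**Working it through.** No figure in the plan can be reproduced here, so the rule was applied to a constructed record.

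**Inputs**
- Ongoing if D07 is at least Grade 1 and the post-D7 maximum is at least Grade 1; otherwise not ongoing (SAP 4.4.1.1.7).
- Overall days = (stop date − vaccination date) + graded days within D0 to D07 − length of solicited period + 1, for ongoing reactions (SAP 4.4.1.1.6).
- Length of the solicited period: 8 days, D0 to D7 inclusive. The SAP does not state this as a number.
- Constructed reaction (assumption): present D5 to D12, stop date D12, true length 8 days.

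**Complete records.** Graded days within the period are D5, D6 and D7, so 3. The reaction is ongoing, and overall days = 12 + 3 − 8 + 1 = 8. This matches the true length, so the formula works with complete data and 8 is the right period length.

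**One record blank**

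| Blank record | Ongoing under 4.4.1.1.7? | Graded days, D0 to D07 | Overall days if the stop date were used |
|---|---|---|---|
| None | Yes | 3 | 12 + 3 − 8 + 1 = 8 |
| Post-D7 maximum | No | 3 | 12 + 3 − 8 + 1 = 8 |
| D07 | No | 2 | 12 + 2 − 8 + 1 = 7 |
| D6 | Yes | 2 | 12 + 2 − 8 + 1 = 7 |

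Only a blank at D07 or in the post-D7 record changes ongoing status; a blank at D6 does not. In the two affected rows the SAP defines no overall duration. If the within-period count is reported in its place, the 8-day reaction appears as 3 days or 2 days.

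**How often.** The documents give no rate of blank records. Suppose each of the two records is blank independently with probability *m*. The share of truly ongoing reactions with exactly one of them blank is 2*m*(1 − *m*):
- *m* = 1%: 2 × 0.01 × 0.99 = 2.0%
- *m* = 2%: 2 × 0.02 × 0.98 = 3.9%
- *m* = 5%: 2 × 0.05 × 0.95 = 9.5%
- *m* = 10%: 2 × 0.10 × 0.90 = 18.0%

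These are shares of reactions that pass D7, not of all subjects. Protocol 1.2.1.2 reports that in MET51 most solicited reactions lasted 1 to 3 days, so the base is probably small.

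**The case against.** **The listed endpoint is not the one affected.** SAP 4.3 lists the number of days of occurrence for solicited reactions, and a reader might infer that this endpoint is shortened. SAP 4.4.1.1.5 defines that term as graded days within D0 to D07, which depends on neither ongoing status nor the stop date. Only the separate overall number of days in 4.4.1.1.6 does. This objection stands.

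**The short durations are not stated in the SAP.** A reader might also infer that the SAP declares these reactions ended by D7 and reports 2 or 3 days as their overall duration. It says only that they are not considered ongoing, and gives no overall duration for such reactions. The day counts need the added assumption that the within-period count is used. The loss of ongoing status does not.

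**The trigger is narrow.** It needs a reaction that passes D7, a blank in one particular record and a complete stop date. The diary is reviewed for completeness at Visit 2 (Protocol 5.1.4.3), gaps are clarified with the family (Protocol 11.1, 13.2), and omissions are checked and queried (Protocol 11.2). These steps make blanks fewer but do not rule them out.

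**Preferring measurement to the flag is a legitimate choice.** That is so, and the fix below keeps it: a recorded grade always takes priority, and the flag alone establishes nothing.

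**Filling in the blank day would break other rules.** Counting a Missing D07 as a reaction day would conflict with the no-replacement rule in SAP 5.3.1 and with SAP 4.4.1.1.4, where a Missing day separates two periods of a reaction. This stands, and the fix does not do it.

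**Conclusion.** The gap is real and minor. When exactly one of the two key grades is Missing and the other is at least Grade 1, SAP 4.4.1.1.7 classes the reaction as not ongoing and disregards a complete stop date after D07. This rests on the text alone. The step from 8 days to 3 or 2 rests on the constructed record and on the within-period count standing in for an undefined value.

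The misclassification can only remove ongoing status, so it understates how many reactions continue past D7. Presence, onset and maximum intensity in the solicited period do not change. A reader might infer that the rule favours the investigational vaccine. The documents do not support that: the same rule applies in all three groups, the safety analysis is descriptive, and a differential effect would need long reactions or blank records to be distributed unevenly, on which there is no information. The immunogenicity tests, alpha and power are untouched.

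**What to change.** Amend SAP 4.4.1.1.7 as follows:

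- Keep the present rule when both grades are recorded. A recorded None at D07 or after D7 still means not ongoing.
- When one grade is Missing, the other is at least Grade 1 and the recorded stop date is after D07, class the reaction as ongoing and apply the 4.4.1.1.6 formula without filling in a Missing D07. The example then gives 8 days with the post-D7 grade blank and 7 with D07 blank, against a true 8.
- When one grade is Missing, the other is not None and there is no complete stop date, set ongoing status and overall days to Missing. This matches how 4.4.1.1.6 already treats a missing stop date.

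The cost is a short SAP edit and a small programming change before database lock; the stop date is already in the SAP's derivations. The downside is that a few durations will rest on the recorded stop date instead of a diary grade, and a footnote can give their number.

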#### 4.4.1.2 Unsolicited Non-serious AEs

#### 4.4.1.2.1 Presence

An observation will be considered an event if it has at least a verbatim term and is not a Grade 0 (None) intensity event.

Grade 0 events will not be included in the analysis of the endpoint, and should be included in the listing "Unsolicited non-serious adverse events not included in the safety analysis."

#### **4.4.1.2.2** Intensity

Intensity for unsolicited non-serious adverse event (AE) will be derived according to the following classification: Grade 0 (None), Grade 1, Grade 2, Grade 3, or Missing (Unknown).

If the unsolicited non-serious AE is measurable and its preferred term is part of the list of solicited reactions, then the measurement is derived based upon and following the same rule than the intensity scales defined in the protocol for that measurable injection site or systemic reaction.

Intensity for the other unsolicited non-serious AEs will correspond to the value reported in the CRF.

The maximum intensity corresponds to the highest intensity for a unique term.

#### 4.4.1.2.3 Last Vaccination

Since there is only one vaccination in this study, last vaccination before an unsolicited non-serious AE is the study vaccination at V01.

#### **4.4.1.2.4** Time of Onset

Time of onset is derived from the start date of the unsolicited non-serious AE provided in the clinical database and the date of last vaccination:

• start date of the unsolicited non-serious AE – date of vaccination

The time of onset should be considered as missing only if one or both of the dates are missing or partially missing.

The unsolicited non-serious AEs will be analyzed "Within 30 days", which corresponds to AEs with a time of onset between 0 and 30 days after vaccination or missing. An AE with missing time of onset will be considered to have occurred just after the vaccination indicated by the visit number, so will be included in these tables.

Note: Unsolicited non-serious AE that occurred before vaccination (negative time of onset) or with a time of onset higher than defined above (i.e., >30 days after vaccination) will not be included in analysis, but will be listed separately.

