#### **4.4.1.3.3** Time of Onset

Time of onset will be computed using the same methodology as for unsolicited non-serious AEs described in Section 4.4.1.2.4.

SAEs (including AESIs) will be analyzed throughout the study using the following periods:

- Within 7 days after vaccination
- Within 30 days after vaccination
- During the study period: from D0 to last visit (i.e., all SAEs [including AESIs] occurred during the study)

An SAE (including AESI) with missing time of onset will be considered to have occurred just after the vaccination indicated by the visit number, so will be included in the safety analysis tables.

Note: SAEs (including AESIs) that occurred before vaccination (negative time of onset) will not be included in analysis, but will be listed separately.

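### A partly known AE or SAE start date is handled as no date at all, so an event whose recorded month rules out a safety window is still counted in it (minor).

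*SAP*

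**What the plan says.** SAP 4.4.1.2.4 defines time of onset for a non-serious unsolicited AE as "start date of the unsolicited non-serious AE – date of vaccination". It adds: "The time of onset should be considered as missing only if one or both of the dates are missing or partially missing". The 30-day tables take in events "which corresponds to AEs with a time of onset between 0 and 30 days after vaccination or missing", on the footing that "An AE with missing time of onset will be considered to have occurred just after the vaccination indicated by the visit number". The same section keeps some events out of the analysis and only lists them: "Unsolicited non-serious AE that occurred before vaccination (negative time of onset) or with a time of onset higher than defined above", meaning beyond 30 days.

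For SAEs and AESIs, SAP 4.4.1.3.3 states: "Time of onset will be computed using the same methodology as for unsolicited non-serious AEs described in Section 4.4.1.2.4". The first of its three reporting periods is "Within 7 days after vaccination"; the others are 30 days and the whole study. An SAE "with missing time of onset will be considered to have occurred just after the vaccination indicated by the visit number", and SAEs with a negative onset time are only listed.

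SAP 5.3.1.5 repeats that an incomplete start date stays missing without imputation, and that such events enter the analysis by the visit at which they were collected. SAP 4.4.1.2.3 and 4.4.1.3.2 note that there is one vaccination, at V01, so the assumed onset can only be D0.

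**The concern.** Assuming D0 is a cautious default when timing is unknown. Here it also applies when timing is partly known and the known part contradicts D0. The SAP's exclusions need a computed onset, negative or above 30 days, and an incomplete date can never give one. An event that the recorded month places before vaccination, or a non-serious AE that it places after D30, therefore stays in the tables. An SAE that the month places after D7 or D30 is counted in an earlier period than the data allow.

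What is at stake is the accuracy of the descriptive safety tables, mainly the short-window SAE and AESI table, where counts are low.

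**Working it through.** The documents give no figure that depends on this rule, so there is none to reproduce. The check has three parts.

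**1. Can the situation arise within follow-up?** V02 falls on D30 to D44, and Protocol 9.3.2.3.3 has parents record events through that period. Take a start date with only month and year known:

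| Vaccination | Recorded start | Bound on onset | Counted as |
|---|---|---|---|
| 25 Jan 2020 | Mar 2020 | earliest 1 Mar = D36 (D44 = 9 Mar) | non-serious AE within 30 days |
| 10 Oct 2019 | Nov 2019 | earliest 1 Nov = D22 | SAE within 7 days (inferred) |
| 10 Oct 2019 | Sep 2019 | latest 30 Sep = D-10 | post-vaccination event |

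The 7-day placement is an inference: SAP 4.4.1.3.3 says that such SAEs enter the safety tables as if they began right after the dose, but does not name the window.

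**2. How often would the month settle it?** Inputs: the planned vaccination period Q3 2019 to Q4 2020 (Protocol 5.1.5), which is 550 dates from 1 Jul 2019 to 31 Dec 2020, and V02 at D30 to D44. Assumptions: vaccination dates and onset days are uniform, only the day of the month is unknown, and the true onset is outside the window. Let a and b be the first and last day of the recorded month, counted from vaccination. Onset is proven late if a > 7 or a > 30, and proven pre-vaccination if b < 0.

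- After D7, every V02 at D44: 37 onset days × 550 = 20,350 cases, of which 12,219 are proven = 60%.
- After D7, every V02 at D30: 23 × 550 = 12,650 cases, 4,968 proven = 39%.
- After D7, V02 uniform over D30-D44, each onset day weighted by the V02 days that reach it: 126,830 / 247,500 = 51%.
- After D30, onset D31-D44, every V02 at D44: 14 × 550 = 7,700 cases, 1,890 proven = 24.5%. With V02 uniform, weighted in the same way, 10,080 / 57,750 = 17%.
- Before vaccination, onset D-30 to D-1: 30 × 550 = 16,500 cases, 8,369 proven = 51%.

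Repeating this for the 365 dates from 1 Sep 2019 gives 60.2%, 39.5%, 51.4%, 24.4% (17.3% with V02 uniform) and 50.9%, so the choice of calendar range hardly matters.

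**3. What does one misplaced child do?** With 235 per group (SAP 5.5), 100 / 235 = 0.43 percentage points. For scale, MET51 had 7 children with an SAE among 918 randomized (Protocol 1.2.1.2). At that rate 705 × 7 / 918 = 5.4 children would have one here.

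**The case against.** The strongest reply is that this is a deliberate and consistent convention. It appears in three sections, follows the general policy of not replacing missing safety data (SAP 5.3.1), errs towards counting, applies alike to all groups, and feeds no hypothesis test. All of that is true. It justifies the default for uninformative dates, but not for dates that exclude D0.

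Other parts of the reply stand and limit the point:

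- The percentages are conditional on an incomplete date and a true onset outside the window. How many such dates to expect is not stated. SAE dates in particular should be nearly complete: Protocol 10 to 10.2 and 11.2 require reporting within 24 hours, supporting records and reconciliation with the pharmacovigilance database. In the other direction, Protocol 5.3.1 kept children in the study during the COVID-19 hold with follow-up possible by telephone, where incomplete dates are plausible.
- A reader might infer that one misplaced SAE distorts about a fifth of the children with an SAE (1 of about 5). It does not: a post-vaccination SAE still counts correctly in the whole-study table, and only its shorter window is wrong.
- A reader might also infer, because SAP 5.3.1.2 sets missing causality to related, that pre-existing conditions will surface as related events just after the dose. That needs several failures at once. Protocol 9.3.2.1 keeps pre-existing conditions out of AE reporting unless they worsen. Protocol 9.3.2.3.5 requires a causality assessment for each unsolicited systemic AE and names onset before vaccination as a ground for not related. Protocol 10.4 adds a Sponsor assessment for SAEs.

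**Conclusion.** The point holds as a minor improvement. The rule misclassifies an event whenever the known month and year exclude the window, and in doing so it overrides the SAP's own exclusion of pre-vaccination events and of non-serious AEs after D30. For SAEs after D30 no exclusion is breached; the fault there is assignment to too early a period.

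Under the uniform-date assumption the month is decisive after D7 for about 39% to 60% of month-only dates, depending on when V02 takes place, and before vaccination for about 51%. For the 30-day window it is at most about 24%, so the documents do not support saying that the data usually prove a late onset there. The unconditional effect cannot be computed without the number of incomplete dates, and is probably small. No primary or secondary conclusion is affected.

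**What to change.** Amend SAP 4.4.1.2.4, 4.4.1.3.3 and 5.3.1.5 together. From the known parts of the start date, derive the earliest and latest possible onset.

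- If the earliest is after a window, leave the event out of that window.
- If the latest is before vaccination, list the event as pre-vaccination.
- Otherwise, or if the date is wholly missing, keep the present rule.

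SAP 5.3.1.5 must be included, or it would contradict the other two sections. It also makes onset missing when only the stop date is incomplete, which SAP 4.4.1.2.4 does not. The two should be reconciled in the same edit.

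The cost is a short text change in three sections, a few lines of code, and a small departure from the sponsor's standard convention. The cautious default remains wherever the date is uninformative.
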